 - Work Productivity and Activity Impairment Questionnaire – Ulcerative Colitis (WPAI-UC)
 - Urgency numeric rating scale (NRS)
 - Abdominal pain NRS
- The proportion of subjects with UC-related hospitalizations
- The proportion of subjects requiring UC-related surgeries, including colectomy

Safety assessments:

Safety will be assessed using monitoring of adverse events, clinical laboratory findings, 12-lead ECGs, physical examinations, vital signs, pulmonary function tests, ophthalmoscopy, and optical coherence tomography.

Safety endpoints:

- Incidence and severity of adverse events
- Incidence and severity of laboratory abnormalities, and change from baseline in laboratory values (to include hematology, serum chemistry, coagulation, and urinalysis)
- Incidence of clinically significant vital sign abnormalities and changes from baseline

Statistical methods:

Sample size

Based on a 2-group Fisher's exact test, a 1-sided significance level of 0.025, and a 2:1 randomization ratio, 420 total subjects (280 etrasimod, 140 placebo) are required to achieve 93.4% power to detect a difference of 13.5% in the primary endpoint of clinical remission at Week 52 between the etrasimod treatment group (23.5%) and the placebo treatment group (10.0%). With this sample size, there will be 96% power to detect a difference of 12.5% in the other primary endpoint of clinical remission at Week 12, assuming a placebo rate at 6.0%. The lower bound of overall power for both primary endpoints (as coprimary endpoints) is at least 90%; and since the two primary endpoints are expected to be at least moderately positively correlated, the actual overall power to reject both of their null hypotheses is likely to be greater than 90%.

Efficacy analysis

The primary analysis of the proportion-based efficacy endpoints will be carried out using the Cochran-Mantel-Haenszel (CMH) method, stratified by (a) naïve to biologic or JAK inhibitor therapy at study entry (yes or no), (b) baseline corticosteroid use (yes or no), and (c) baseline disease activity (MMS: 4 to 6 or 7 to 9). Results will be expressed as the number of subjects in remission, remission percentages, difference in remission percentages, odds ratio, and associated 95% confidence intervals (CIs) and p-values.

Testing strategy

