10.11. Safety Endpoints

- Incidence and severity of adverse events
- Incidence and severity of laboratory abnormalities, and change from baseline in laboratory values (to include hematology, serum chemistry, coagulation, and urinalysis)
- Incidence of clinically significant vital sign abnormalities and changes from baseline

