10.12.2. Safety Analysis

All safety data will be listed and summarized by treatment group. All TEAEs will be coded using the latest version of MedDRA and tabulated by System Organ Class and Preferred Term. Incidence of adverse events, SAEs, and adverse events leading to discontinuation will be summarized and presented in descending order of frequency. Associated laboratory parameters such as hepatic enzymes, renal function, and hematology values will be grouped and presented together. Individual subject values will be listed and values outside of the standard reference range will be flagged. Shift tables and analyses of changes from baseline will be produced. The change from baseline for each of the vital signs and 12-lead ECG parameters will be summarized. Incidence of abnormal vital signs parameters and outlier 12-lead ECG results will be tabulated.

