18.1.1.1. Severity

Severity is classified as Grade 1: Mild, Grade 2: Moderate, Grade 3: Severe, Grade 4: Life-threatening, Grade 5: Death related to AE, using the Common Terminology Criteria for Adverse Events, v5.0 (CTCAE v5.0).

All TEAEs will be summarized by SOC, PT, and maximum severity, with SOC and PT presented by descending frequency. If a subject reports a TEAE more than once within a SOC/PT, the AE with the worst-case severity will be used in this summary.

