18.3.1. Safety Laboratory Evaluations

Hematology, serum chemistry, coagulation, and urinalysis are analyzed and reported by central laboratory and sometimes by local laboratory. Results out of reference range are flagged by the performing laboratory (eg, low, high). A full list of laboratory assessments to be included in the outputs is included in Clinical Study Protocol APD334-301 Table 6.

In general, presentations will use SI units. Quantitative laboratory measurements reported as “< X” or “> X”, where X may be the lower limit of quantitation (LLQ) or the upper limit of quantitation (ULQ), respectively, will be converted to X for the purpose of quantitative summaries, but will be presented as recorded, ie, as “< X” or “> X” in the listings. For urinalysis, only pH and specific gravity are considered as quantitative tests. If local and central laboratory assessments are available from the same day, central laboratory assessments will be used in the summary as per Section [6.4](#).

The following summaries will be provided for laboratory data:

- Value and change from Baseline by visit (for hematology, serum chemistry, quantitative urinalysis [pH and specific gravity], and coagulation)

- Incidence of abnormal values according to laboratory reference ranges by visit
- Incidence of lymphocytes $< 0.2 \times 10^9/L$, $0.5 \times 10^9/L$, or neutrophils $< 0.5 \times 10^9/L$, $1 \times 10^9/L$ at end of treatment and anytime in the study
- Shift from end of treatment to each follow-up visit in incidence of lymphocytes in normal range and in incidence of lymphocytes of at least 80% percent of Baseline, by visit (2-Week Follow-Up, 4-Week Follow Up, and Last Follow-Up)
- Shift from Baseline to end of treatment according to laboratory reference range (for quantitative measurements and categorical measurements)
- Evaluation of drug-induced serious hepatotoxicity (eDISH) plots for the following laboratory assessments (using values after the first administration of study treatment):
 - Maximum aspartate aminotransferase (AST) versus same-day total bilirubin
 - Maximum alanine aminotransferase (ALT) versus same-day total bilirubin
 - Maximum gamma-glutamyl transferase (GGT) versus same-day total bilirubin
 - Maximum alkaline phosphatase (ALP) versus same-day total bilirubin

The eDISH plots above will be repeated with adjustment for elevated Baseline.

- Incidence of hepatic enzyme elevations by visit

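### The protocol makes severity of laboratory abnormalities a safety endpoint, but outside lymphocytes, neutrophils and liver tests the SAP plans no severity categories and no worst post-Baseline table

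*Protocol*

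**What the plan says.** The protocol synopsis (Safety endpoints) and Protocol 10.11 word the endpoint identically: "Incidence and severity of laboratory abnormalities, and change from baseline in laboratory values (to include hematology, serum chemistry, coagulation, and urinalysis".

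Protocol 10.12.2 describes the laboratory analysis as listings, shift tables and analyses of change from baseline. On abnormal values it says "Individual subject values will be listed and values outside of the standard reference range will be flagged". It names no severity scale for laboratory values.

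SAP 18.3.1 starts from the laboratory's own flag: "Results out of reference range are flagged by the performing laboratory (eg, low, high". For the general panel it then plans three summaries:
- A continuous summary, given as "Value and change from Baseline by visit (for hematology, serum chemistry, quantitative urinalysis [pH and specific gravity], and coagulation".
- A count of abnormal results, given as "Incidence of abnormal values according to laboratory reference ranges by visit".
- A shift table, given as "Shift from Baseline to end of treatment according to laboratory reference range (for quantitative measurements and categorical measurements".

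The same section adds cut-offs for lymphocytes and neutrophils, bands in multiples of the upper limit of normal for ALT, AST, total bilirubin, ALP and GGT, and eDISH plots. All laboratory values are listed.

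The only severity scale in the SAP is in 18.1.1.1, where adverse events are graded "using the Common Terminology Criteria for Adverse Events, v5.0 (CTCAE v5.0".

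**The concern.** Incidence, severity and change from baseline are three separate parts of one endpoint. For most tests the SAP has a table for the first and the third but none for the second. In a reference-range table, a value just below the lower limit and one far below it fall in the same cell. If the two arms had similar out-of-range rates but differed in how extreme the values were, no planned laboratory abnormality table would separate them for hemoglobin, platelets, creatinine, potassium, creatine kinase or clotting times. If cut-offs were then chosen after unblinding to fill the gap, the choice would be open to question.

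**Working it through.** No power or error-rate calculation applies. The check is to set the endpoint beside every laboratory output in SAP 18.3.1, then count tests.

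**1. Which outputs separate mild from severe?**
- Lymphocytes (below 0.2 and 0.5 × 10⁹/L) and neutrophils (below 0.5 and 1 × 10⁹/L), at end of treatment and at any time: yes.
- ALT, AST, total bilirubin, ALP and GGT in multiples of the upper limit of normal, with eDISH plots of maxima: yes.
- Reference-range incidence by visit: no.
- Reference-range shift from Baseline to end of treatment: no.
- Value and change from Baseline by visit: this describes the distribution and is the endpoint's third part, not a count of subjects by severity.
- Listings: values by subject, flagged only as outside the range.

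**2. How many tests are affected?** From Protocol Table 6:
- Serum chemistry: 26 tests listed, 5 with graded bands, so 26 − 5 = 21 without.
- Coagulation: 3 listed, 0 graded.
- Urinalysis: 12 items listed, 0 graded.
- Hematology: only the lymphocyte and neutrophil parts of the differential have cut-offs. Hemoglobin, platelets and total white cells have none.

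Not every item lends itself to a grade, so these counts are an upper limit on the number of missing severity tables.

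**3. What happens to a transient abnormality?** The shift table looks only at end of treatment, so a value that worsens and recovers before then is not in it. SAP 6.3 says all measurements are considered in abnormality summaries and worst-case values, so the episode can still be counted in the by-visit incidence table, but without its depth. SAP 18.3 refers to deriving maximum, minimum or worst values, yet 18.3.1 tabulates none for these tests.

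**4. How are the other safety domains treated?** The SAP predefines markedly abnormal criteria for ECG (18.4.1), vital signs (18.5.2) and pulmonary function (18.7.1.1). ECG interpretation also gets a shift to the worst post-Baseline result (18.4). Among these domains, only the laboratory endpoint names severity in the protocol, and it has no such general criteria.

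**5. Does adverse event grading fill the gap?** Protocol 9.10.7 requires the investigator to review each laboratory report and record clinically relevant changes as adverse events. These are graded by CTCAE v5.0 (Protocol 9.10.8.1.5) and tabulated by maximum severity (SAP 18.1.1.1). Three features keep this from standing in for the endpoint:
- Adverse events are a separate endpoint in Protocol 10.11.
- Protocol 9.10.7 sets aside findings associated with the underlying disease unless they are judged more severe than expected. A low hemoglobin attributed to colitis may therefore never be graded.
- After randomization, investigators do not see white cell and differential counts (Protocol 9.8.4 and Table 6 footnote a). The unblinded monitor's stated triggers for notifying them are a neutrophil count below 1000 and a lymphocyte count below 200 cells/µL. For total white cells this route is largely closed.

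**The case against.** The strongest reply is that the SAP carries out what Protocol 10.12.2 asks for and adds thresholds where the drug's mechanism points (lymphocytes and liver). Continuous summaries are planned by visit for all four panels, limited to pH and specific gravity in urinalysis. SAP Appendix 1 gives reporting precision for minimum and maximum, so an extreme value should be visible by arm and visit. Every value is listed, and recording clinically relevant changes as adverse events is mandatory.

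Much of this stands, and it rules out four stronger readings that a reader might infer.
- *Severity cannot be reported.* Some of it will be, through graded adverse events, and the values needed to grade the rest are collected.
- *The SAP only counts values in or out of range.* That describes the abnormality counts and shift tables, not the whole of 18.3.1.
- *SAP 3.3 hides a dropped analysis.* Protocol 10.12.2 never specified a severity table, so no planned analysis was removed. The tension begins inside the protocol, between 10.11 and 10.12.2, and the SAP leaves it unresolved.
- *A graded table would turn noise into a signal.* Suppose three severe values in all, every one on etrasimod, with 280 and 140 subjects. The chance of that split with no drug effect is (280 × 279 × 278)/(420 × 419 × 418) = 0.295. Such a table would make the cases visible without being conclusive. Nor do the documents give a background out-of-range rate for these patients, who have active colitis and may enter with hemoglobin as low as 8 g/dL.

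What the reply does not supply is a by-arm count of subjects by severity. A maximum shows one subject's value, not how many subjects reached a given level, and a listing is not a summary.

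**Conclusion.** The gap is real and of moderate weight. For every laboratory test other than lymphocytes, neutrophils and the five liver tests, no planned laboratory table reports abnormalities by severity, and none reports the worst post-Baseline value. The endpoint in Protocol 10.11 is therefore only partly delivered. The size is best stated as coverage: up to 21 of 26 chemistry tests, all 3 coagulation tests, all 12 urinalysis items, and most of hematology. No claim is made about how many severe abnormalities would be missed, because the documents give no rates from which to estimate that. The conclusion assumes that severity in the endpoint means severity of the laboratory abnormality itself. If the sponsor meant adverse event grade, neither document says so.

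**What to change.** In SAP 18.3.1, grade post-Baseline central laboratory values by CTCAE v5.0 where that scale has a numeric grade. Tabulate by arm (a) the worst post-Baseline grade and (b) the shift from Baseline grade to worst post-Baseline grade. Use scheduled, unscheduled and early termination samples. Keep the existing reference-range, continuous, lymphocyte, neutrophil and liver outputs.

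The SAP should list the tests to be graded and their cut-offs. Protocol 9.10.8.1.5 gives only general grade descriptions, so neither document shows which tests have numeric grades.

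The cost is SAP wording and a few more descriptive tables. CTCAE v5.0 is already the trial's adverse event scale, and no new samples or data are needed. Setting the cut-offs before unblinding avoids choosing them afterwards.

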|--------------|-----------------------------------------------------|
| ADL | activities of daily living |
| ADR | adverse drug reaction |
| ALC | absolute lymphocyte count |
| ALT | alanine aminotransferase |
| ANC | absolute neutrophil count |
| 5-ASA | 5-aminosalicylic acid |
| AST | aspartate aminotransferase |
| AV | atrioventricular |
| AZA | azathioprine |
| β-hCG | beta-human chorionic gonadotropin |
| BP | blood pressure |
| CBC | complete blood count |
| CD | Crohn's disease |
| CFR | Code of Federal Regulations |
| cGMP | Current Good Manufacturing Practices |
| CMH | Cochran-Mantel-Haenszel |
| CMP | clinical monitoring plan |
| CRO | contract research organization |
| CRP | C-reactive protein |
| CTCAE | Common Terminology Criteria for Adverse Events |
| CYP | cytochrome P450 |
| DLCO | diffusing capacity of the lungs for carbon monoxide |
| DMC | Data Monitoring Committee |
| ECG | electrocardiogram |
| eCRF | electronic case report form |
| eDiary | electronic diary |
| EIMs | extraintestinal manifestations |
| ES | endoscopic score |
| ET | End-of-treatment |
| FAS | Full Analysis Set |
| FDA | Food and Drug Administration |

| Abbreviation | Definition |
|---------------------|----------------------------------------------|
| FEV ₁ | forced expiratory volume at 1 second |
| FVC | forced vital capacity |
| GCP | Good Clinical Practice |
| HbA1c | hemoglobin A1c |
| HBsAg | Hepatitis B surface antigen |
| HBV | Hepatitis B virus |
| HCV | Hepatitis C virus |
| HIV | human immunodeficiency virus |
| HR | heart rate |
| HRQoL | health-related quality of life |
| hs-CRP | high-sensitivity C-reactive protein |
| IB | Investigator's Brochure |
| IBD | inflammatory bowel disease |
| IBDQ | Inflammatory Bowel Disease Questionnaire |
| ICF | informed consent form |
| ICH | International Council for Harmonisation |
| IEC | Independent Ethics Committee |
| IGRA | interferon-gamma release assay |
| IND | Investigational New Drug |
| IRB | Institutional Review Board |
| IUD | Intrauterine device |
| IV | intravenous |
| IWRS | Interactive Web Response System |
| JAK | Janus kinase |
| MAR | missing at random |
| MCS | Mayo clinic score |
| MDR | multi-drug resistant |
| MedDRA | Medical Dictionary for Regulatory Activities |
| mFAS | modified Full Analysis Set |
| MMF | mycophenolate mofetil |
| MMS | modified Mayo score |
| 6-MP | 6-mercaptopurine |

| Abbreviation | Definition |
|---------------------|------------------------------------------------------------------------------|
| NF | National Formulary |
| NRS | numeric rating scale |
| NSAID | nonsteroidal anti-inflammatory drugs |
| OCT | optical coherence tomography |
| OLE | open-label extension |
| PFT | pulmonary function test |
| PGA | Physicians Global Assessment |
| Ph. Eur. | European Pharmacopoeia |
| PK | pharmacokinetics |
| PML | progressive multifocal leukoencephalopathy |
| PPD | purified protein derivative |
| QTcF | Fridericia's corrected QT interval |
| RB | rectal bleeding |
| S1P | sphingosine 1-phosphate |
| SAE | serious adverse event |
| SAP | statistical analysis plan |
| SF | stool frequency |
| SF-36 | Medical Outcomes Study 36-Item Short Form Health Survey |
| SOP | Standard Operating Procedures |
| TB | tuberculosis |
| TMF | trial master file |
| TNF α | tumor necrosis factor alpha |
| TST | tuberculin skin test |
| UC | ulcerative colitis |
| UC-PRO/SS | Ulcerative Colitis Patient-Reported Outcomes Signs and Symptoms |
| ULN | upper limit of normal |
| USP | United States Pharmacopeia |
| WBC | white blood cell |
| WPAI-UC | Work Productivity and Activity Impairment Questionnaire – Ulcerative Colitis |

1. INTRODUCTION

1.1. Ulcerative Colitis

Inflammatory bowel disease (IBD) describes conditions with chronic or recurring immune response and inflammation of the gastrointestinal tract. There are 2 major types of IBD: Crohn's disease (CD) and ulcerative colitis (UC). These are chronic recurrent, remittent, or progressive inflammatory conditions that may affect the entire gastrointestinal tract (CD) and the colonic mucosa (UC), and are associated with an increased risk for colon cancer (Kaser 2010).

Ulcerative colitis is characterized by diffuse mucosal inflammation limited to the colon and involves the rectum in approximately 95% of cases and may extend proximally in a symmetrical, circumferential, and uninterrupted pattern to involve parts or all of the large intestine (Kornbluth 2010). Symptoms for UC can vary, depending on the location and severity of inflammation, but some of the most common are diarrhea, abdominal cramps, and rectal bleeding. The hallmark clinical symptom is bloody diarrhea often with prominent symptoms of rectal urgency and tenesmus (Kornbluth 2010).

Treatment for subjects with UC is generally for symptomatic care (relief of symptoms) and mucosal healing and includes 5 major classes of medications: 5-aminosalicylic acid (5-ASA), antibiotics, corticosteroids, immunomodulators, biologic therapies (eg, tumor necrosis factor [TNF] inhibitors and anti-integrins) and most recently Janus kinase (JAK) inhibitor therapy. These drugs may be prescribed in a "step-up" approach, with escalation of the medical regimen until a response is achieved, or a "step-down" manner, with initiation of treatment with biologics and immunomodulators (Rowe 2020).

An unmet medical need exists for the development of targeted therapies for the treatment of UC with easily administered and stable oral drugs, particularly as most patients treated with biologics experience inadequate responses. Moreover, many patients who receive biologics lose responsiveness over time, even though their initial response may have been positive (Ungar 2016).

1.2. Etrasimod

Etrasimod (APD334) is an orally administered, selective, synthetic sphingosine 1-phosphate (S1P) receptor 1, 4, 5 modulator that is being developed to treat immune-mediated inflammatory disorders, including UC.

The S1P₁ is a cell surface expressed protein that has been shown to regulate lymphocyte migration out of lymphoid tissues (Brinkmann 2010). Synthetic small molecule S1P₁ agonists have been observed to act as functional antagonists by inducing sustained receptor internalization, thus inhibiting lymphocyte migration out of lymphoid tissues and lowering the amount of peripheral blood lymphocytes available to be recruited to sites of inflammation. Modulation of the S1P/S1P receptor axis is thought to be a potential therapeutic approach to the management of immune-mediated inflammatory disorders (Nielsen 2017); as such, etrasimod is expected to potentially provide therapeutic benefit to patients with UC. A Phase 2 study with etrasimod in subjects with moderately to severely active UC demonstrated consistent and clinically meaningful improvements in endpoint measures reflecting cardinal symptoms of UC and objective findings of endoscopic improvement (Sandborn 2020). Refer to the current edition

of the Investigator's Brochure (IB) for a complete summary of the clinical and nonclinical data relevant to the investigational product and its study in human subjects.

1.3. Benefit/Risk Assessment

Considering the significant unmet need for safe and effective, orally administered treatments for UC, etrasimod may potentially provide therapeutic benefit via S1P receptor modulation.

Adverse events that have been reported with S1P receptor modulators include bradycardia at the first dose or atrioventricular (AV) block, macular edema, hypertension, headache, cough, dyspnea, back pain, influenza, and diarrhea.

Safety and tolerability of etrasimod has been evaluated in Phase 1 studies with healthy adult subjects at single doses up to 5 mg and repeated doses up to 4 mg once daily. Repeated doses of 2 mg have been evaluated in Phase 2 studies of subjects with moderately to severely active UC (refer to the current edition of the IB). Etrasimod was found to be safe and well tolerated in these studies, with no clinically significant safety concerns with respect to vital signs, electrocardiograms (ECGs), pulmonary function tests (PFTs), ophthalmoscopy, or clinical laboratory tests. Etrasimod produced a dose-dependent sustained decrease in total lymphocyte count, which is expected given etrasimod's mechanism of action. Lymphocyte counts were within normal limits by 7 days after the last dose.

Detailed information regarding the known and expected benefits and risks and reasonably expected adverse events of etrasimod can be found in the IB.

Based on the mechanism of action of etrasimod and prior experience with other agents acting via a similar mechanism, monitoring for specific safety parameters are planned for this study, which include: auscultation of the lungs as part of the physical exam; PFT, exclusion of subjects with macular edema or retinopathy, with assessment of optical coherence tomography (OCT) occurring throughout the study; and exclusion of subjects with certain cardiac risks, with assessment of vital signs in the period following dosing.

- Auscultation of lungs will be conducted as part of the physical examination.
- Prospective subjects with a history of macular edema or retinopathy will be excluded from the study. All randomized subjects will be assessed by OCT at study entry, periodically throughout the treatment period, and as clinically indicated any time during the study.
- Subjects with certain cardiac risks will also be excluded from the study. Randomized subjects will be monitored in a period following dosing, and vital signs will be assessed for determination of the subject's health before discharge. Subjects requiring follow-up monitoring will be evaluated in the clinic until cardiac variances return to acceptable levels.

Based on the preclinical and clinical data that has been generated from etrasimod studies and the precautions outlined above, the favorable benefit/risk assessment justifies the further clinical development of etrasimod in subjects with moderately to severely active UC and the current Phase 3 study.

The current study is a Phase 3 multicenter, randomized, double-blind, placebo-controlled study to evaluate the efficacy and safety of etrasimod in subjects with moderately to severely active UC. Subjects who complete the total 52-week treatment or subjects with worsening disease after the Week 12 visit assessments (Section 5.1.1) will have the opportunity to enroll into an open-label extension (OLE) study that will provide additional information on the long-term efficacy and safety of etrasimod. The results from this study will be used to support the regulatory approval of etrasimod for the treatment of patients with UC.

